The 3-AAT Observation ethogram, adapted with permission from Johns Hopkins University, was used to code both canine and human interaction during AAT sessions. The revised ethogram appraises the frequency of six domains of human interaction (affection, play, care, communication, comfort, withdrawal) and 24 subdomains of human behavior that can occur in an AAT session. The ethogram assesses the frequency, intensity, and duration of the interactions between the canine and child. Frequency is measured by a tally count and duration is assessed by rounding either up or down to the nearest 30 second mark. Each interaction has a code for intensity from 0 (not intense) to 3 (the most intense), and the mode of the interaction was entered to run the analysis.

The Strengths and Difficulties Questionnaire (SDQ) is a 25-item tool developed to assess five domains: Emotional Problems, Conduct Problems, Hyperactivity, Peer Problems, and Prosocial. The SDQ is the most used instrument in measuring therapeutic effect of interventions within the emotional state in children and adolescents ages 2 to 18 years, demonstrating reliable internal

consistency and validity. The SDQ has two versions, one to be administered at the initiation of therapy and then a follow-up version that includes two additional questions examining the impact of the therapeutic intervention. Scores from four behavioral domains range from zero (“normal”) to 10 (“very high concerns”), while Prosocial domain scores are reversed so that 10 indicates “normal” behavior and zero signifies “very high concerns”. The SDQ also assesses the total, impact, internalizing, and externalizing scores to provide a complete overview of the child’s behavior during the past four weeks. Total scores are the sum of the behavior domains except the Prosocial domains and range from zero (normal) to 40 (very high). Impact scores range from zero (normal) to 10 (very high) and reflect overall distress and impairment interfering with daily social interactions. Internalizing scores reflect the Emotional Problems and Peer Problems domains, while Externalizing scores are the sum of the Conduct Problems and Hyperactivity domains. Both the Internalizing and Externalizing domain scores range from zero (normal) to 20 (very high). The initial SDQ was administered at the beginning of the study and the follow-up assessment was used subsequently every four weeks until the study concluded.

Lastly, the Positive and Negative Affect Schedule (PANAS) was administered weekly to measure therapeutic effects occurring in everyday life outside of the AAT session. The PANAS is a 20-item questionnaire utilizing a 5-point Likert scale to assess positive and negative affect occurring the week prior to administration. Each domain has 10 items with scores ranging from 10 to 50, with lower scores reflecting lower levels of positive or negative affect and higher scores signifying higher positive or negative affect. Total scores on each scale are obtained by adding the scores for each item. Analysis of the PANAS demonstrates very good internal consistency reliability, with alphas ranging from 0.86 to 0.90 for Positive affect and from 0.84 to 0.87 for Negative affect.

Protocol Number: 2307483365
Investigator: [name]

Expiration Date: 10/10/2025
Last Approval Date: 10/11/2024

University of Arkansas System

Document Overview

Description: Human animal interaction between children and a live canine or toy plush dog
Explanation:
Organization Doc Num:

Protocol Summary

Protocol Number: 2307483365
Sequence Number: 3
Status: Active - Open to Enrollment
Expiration Date: 10/10/2025
Last Approval Date: 10/11/2024
Investigator: [name]

Protocol Details

Type: Expedited
Summary/Keywords:
Application Date: 09/21/2024
Reference ID1:
Reference ID2:
FDA Application No:
Title: Human animal interaction between children with ASD and a live canine or plush toy dog

Areas of Research

Code	Description
000001	All Research Areas

Organizations

Type	Organization	Address
Performing Organization	University of Arkansas	University of Arkansas [name] USA

Funding Source

Type	Number/Code	Source	Title
Internally Funded/ Unfunded Research	unfunded	N/A	

Protocol Number: 2307483365
Investigator: [name]

Expiration Date: 10/10/2025
Last Approval Date: 10/11/2024

Subjects

Subject	Count
Children	150

Investigators

Person Name: [name] **Role:** Principal Investigator
Units: CC012723 UAF | NURS | Department of Nursing **Affiliation:** Supervisor
Office [contact] **Mobile:**
Email: [contact]

Study Personnel

Person Name	Role	Affiliation	Email
[name]	Study Personnel	Non-Faculty	[contact]
[name]	Study Personnel	Student Investigator	[contact]
[name]	Study Personnel	Student Investigator	[contact]
[name]	Study Personnel	Student Investigator	[contact]
[name]	Study Personnel	Faculty	[contact]
[name]	Study Personnel	Student Investigator	[contact]

Training

Person Name	Description	Date Completed	Expiration Date
[name]	CITI, Basic/Refresher Course - Human Subjects Research, Biomedical Research, Basic Course, 1	02/21/2025	02/21/2028

Other Roles

Person Name	Role	Affiliation	Email
[name]	Data Integrity Manager	Faculty	[contact]

Questionnaire

- **What is the purpose of this research? Please explain both why you are doing the research (class assignment, thesis, etc.) AND/OR state your hypothesis. See attachment is not a sufficient response.**

The proposed project will investigate the human-animal interaction (HAI) and bond (HAB) between a canine trained in therapy techniques or a canine plush toy and youth with autism spectrum disorder (ASD) or developmental delay (DD) during animal-assisted therapy (AAT) sessions. The purpose of this study is to explore identified gaps in knowledge pertaining to AAT in pediatric ASD and DD care management. Specifically, we seek to document human interaction between either a live canine or the plush toy canine during AAT sessions, evaluating prosocial behaviors observed during and after AAT sessions. This study will address the following research questions: 1. How do children with autism ages 2 to 18 years interact with a live canine during AAT sessions? 2. How do children with autism ages 2 to 18 years interact with a toy plush dog during AAT sessions? 3. Is there a difference in HAI in the live canine group and the toy plush dog group? 4. Is there a difference in prosocial behavior observed during AAT sessions between the live canine group and the toy plush dog group? 5. Is there a difference in behavior after AAT sessions between the live canine group and the toy plush dog group?

- Are you collecting data about living individuals?

Yes

- Are you collecting data through intervention or interaction with these individuals?

Yes

- Beyond the basic Participant Types (children, UofA Students, adults, etc.) named elsewhere in this application, do you have a target population (particular group of people) you want to recruit? Some examples might be students in a particular class, members of a particular group or network, people in a specific age range (whether adult or minor), children in a particular school or class, etc.

Yes

- **Describe your target population.**

[name] collaborates with the local primary care providers who refer children, ages 18 months to 18 years, at risk for developmental delay or autism spectrum disorders to the Access for Autism (A4A) program for further developmental evaluation and care management. Children receiving care management by the A4A program who have developmental or behavioral concerns can volunteer to enter this study.

- How are you recruiting participants? Are you standing in a public place asking people to take a survey, sending out introductory emails, posting an ad or blurb on a website or social media, posting a flyer in a public location, etc.? **Please note that all recruitment materials will need to be uploaded in the Notes and Attachments section.

[name] will discuss the study with parents/guardians whose children have been referred to the A4A program for further developmental evaluation. Participation in the study is voluntary and does not affect other services provided by the A4A program.

- **Provide a brief description of the procedures involving the participants.**

Participants will be divided into 2 groups: one group will interact with the live canine while the other group will interact with a toy plush dog identical to the canine. [name] will use a variety of behavioral and developmental evaluations to identify concerns and provide strategies for home therapy to improve delays for both groups. The O'HAIRE Coding System and 3 AAT Observation ethogram will be used to observe and code human behavior during all sessions for both groups. Additionally, participants ages 8 years and older who are cognitively capable will be asked to self-report their emotional state before and after each AAT session using an 11-point Likert scale chart in the shape of a thermometer, with ranges from "no distress/totally relaxed" to "highest anxiety/stress that you've ever felt." A caregiver satisfaction and perspectives of AAT integration in therapy sessions will be assessed via surveys. Demographic data including participant age, gender, race/ethnicity, referral source, prior medical diagnoses, age of ASD or DD diagnosis, medications, and prior allied health or psychological therapies will be collected on all participants. [name] will incorporate AAT into the therapy sessions at the A4A clinic that are guided by the developmental, adaptive-functioning, and social/emotional assessments to target gross and fine motor skill, language, social, emotional, and adaptive-functioning development. Parents will be given handouts that are designed to address deficits identified by the assessments. The O'HAIRE Coding System will be used to observe and code human behavior during AAT sessions. Observable behaviors categories captured by the OHAIRE Coding System include Interactive Behaviors (Social Communication & Environmental Interaction), Emotional Display (Facial, Verbal), and Interfering Behaviors (Aggression, Overactivity, Isolation). The OHAIRE-V3 assessment will be used to calculate a human-animal bond score to quantify the interactions taking place between the pediatric participants and the animal. The ELAN Coding software will be used to achieve high inter-rater reliability through precise timing of observed interactions. The 3 AAT Observation ethogram assesses 26 canine behaviors during human-animal interactions. The ethogram is divided into three categories: affiliative indicators, moderate stress indicators, and high-stress indicators. All sessions will occur at the A4A clinic, which is located on campus in the Epley Center for Healthcare Professionals. The first interaction between the canine and the participant will focus on introducing the two and facilitating a bond through play, such as petting or brushing the canine, or throwing a ball. The canine will be present to interact with children as they are learning their skill for that week. For example, the canine will interact with the participant while the participant is learning a new skill, such as improvement in handwriting, and the participant will be able to interact and play with the canine if the participant focuses on completing the therapy assignment. Likewise, participants will earn points if they perform their therapy strategies at home and can use those points to interact and play with the canine at their next therapy session. Plush dog toys who look like the canine will be given to pediatric participants in both groups as incentive to perform their home therapies.

- **How long are the procedures likely to take? Include duration and frequency.**

The A4A weekly therapy sessions will last about 30 to 60 minutes, with opportunities for participants to interact with the canine or toy plush dog intermittently throughout the session, depending on the therapy activity.

- **How will information be given to people to get their informed consent to participate in this research? Answers should include specific methods (e.g., verbal consent, information handout, online consent form, full consent form requiring signature documentation.) **Please note that consent materials -- from a script for verbal consent to full consent forms that require participant signature -- must be uploaded in the Notes and Attachments section.**

[name] will contact parents/guardians of potential participants to explain the AAT program and gage their interest. If interested, parents will come to the A4A clinic on the first floor of ECHP to meet the canine and sign the informed consent form. Verbal assent will be obtained from pediatric patients who are cognitively able to give it.

- **Does data collection rely on a scheduled event, such as a convention or specific date?**

No

- **How will your data be collected? Include all that apply: online, on paper/in person, audio and/or video recordings. **Please note that all data collection materials will need to be uploaded in the Notes and Attachments section. This includes: surveys, questionnaires, interview questions or anything that is given to or asked of a participant.**

Data will be collected in the initial consultation form for the A4A clinic, through performing developmental, behavioral, social/emotional, and adaptive-functioning assessments, and with surveys. The following will be used to collect data: 1. A4A Intake form: all participants 2. Developmental screenings such as Ages and Stages Questionnaire- 3rd edition: 1 month to 5.5 years; Ages and Stages Questionnaire: Social/Emotional- 2nd edition: birth to age 6 years; Social and Emotional Assessment/ Measure: 2 to 66 months; Strengths and Difficulties Questionnaire: 3 to 16 years; Positive and Negative Affect Schedule: 9 to 14 years; Vineland- 3rd edition: 3 to 21 years; Social Responsiveness Scale- 2nd edition: 2.5 to 18 years; Standford-Binet IQ Test: 2 to 18 years; Autism Diagnostic Observation Scale-2: 18 months to adulthood; and Childhood Autism Rating Scale- 2: 2 years to adulthood. All AAT sessions will be recorded after receiving consent from families to retroactively code participant behavior during sessions with the OHAIRE and 3 AAT ethograms.

- **How will your data be stored? Include all that apply: electronically, on paper, audio and/or video recordings.**

Survey data will be stored in an Excel spreadsheet and Qualtrics, which is a HIPAA-secured software with which caregivers of youth with complete on a personal device (iPad, laptop, cellphone).

- **How will that data be kept secure?**

Data saved in the Excel spreadsheet will only be accessible by approved research staff and stored in [name] password protected laptop. Any hard-copy measures of documents will be stored in Drs. [name]'s locked office in a locked filing cabinet. Video files will be downloaded from camcorders directly to [name] secured laptop. Only authorized research personnel will have access to these files and only participant numbered IDs will be included on assessment documents. Participant identifying information and associated ID numbers will be stored in [name] lab in a password protected computer on a password protected document. [name] and approved research personnel will have access to participant ID information but will mainly utilize participant ID numbers. All video files will be downloaded to [name] computer within 24 hours and then immediately deleted from the camcorder device. Video files will be stored on a password-protected computer as password-protected documents.

- **Minimal Risk is defined as risks of harm not greater than those ordinarily encountered in daily life or during the performance of routine physical or psychological examinations or tests. Will participants be exposed to more than minimal risk? Include in your consideration the potential of mental risks if asking sensitive questions, or legal or reputational risks in case of breach of confidentiality.**

Yes

- **Describe the risks in question and any precautions that will be taken to minimize those risks.**

Participants will not be exposed to more than minimal risks while receiving developmental or behavioral evaluations. Participants will be exposed to the canine during therapy sessions. The canine will be removed if signs of fatigue, fright, or irritation appear. He is trained off leash and will be wearing a harness which can easily be tethered to his crate as needed. [name] will assess the disposition of the pediatric participants before allowing the canine to come to the room and will not allow the canine to participant if the pediatric participant's behavior is disruptive or potentially

dangerous for the canine. [name] is the canine's trained handler and is educated in observing his behavior and will place him in the crate if he appears fatigued or irritated, or if the participant no longer wants to play or pet him.

- **Are there any direct benefits to the participants for participating in this study?**

Yes

- **Describe the benefits participants will or may receive.**

Pediatric participants will receive one plush toy that looks like the canine or toy plush dog they are working with.

- **Will the proposed research involve deception or the withholding of information from participants?**

No

- **Will the proposed research necessitate medical clearance from a physician prior to participation?**

No

- **Will the proposed research involve gathering biological samples (blood, tissue, etc.)?**

No

- **Will the proposed research involve administering of substances or providing food and drink, other than water, to participants?**

No

- **Will the proposed research involve physical exercise or conditioning?**

No

- **Does the research require review by a non-UofA IRB?**

No

- **Does this research require approval from another institution or agency, such as a school or privately owned business?**

No

Protocol Number: 2307483365
Investigator: [name]

Expiration Date:
Last Approval Date: 10/11/2024

New/Changed Attachments

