Participants were divided into two groups: one with a therapy canine and one with a plush toy dog. Therapy sessions lasted 30 to 45 minutes, depending on the age and ability of the participant. All participants, no matter their group, received the same therapeutic strategies, such as sensory integration therapy and seated activity with the therapist, who is a certified pediatric nurse practitioner. Sessions with the therapy canine started with five to 10 minutes of free play with the canine, followed by sensory integration therapy based on the child's identified sensory profile. Participants then entered the clinic room for 20 to 30 minutes of a seated activity in which the therapist who taught coping and socialization strategies to participants and caregivers. Sessions concluded with five minutes of play with the canine. Play activities include fetch, soccer, hide and seek, and puzzles. The canine was trained to lay under the table in the clinic room while the therapist was working with the participants. He would provide grounding, light pressure, and deep pressure therapy if the participant became anxious during the sessions. The seated work was recorded using two cameras to ensure visibility of the interactions between the participant and therapist, canine, and caregiver; participant vocalizations and verbalizations; and participant facial expressions. We used two human-animal ethograms to code behavior during sessions and two behavioral assessments to note behavior occurring after sessions. All sessions occurred in the clinic located on the university's campus. Demographic data including participant age, gender, race, ethnicity, referral source, prior medical diagnoses, age of ASD diagnosis, medications, and prior allied health, school, or psychological evaluations. The canine was certified as a therapy dog and service dog certified in 10 ASD service dog tasks at the time of the study. The canine was present during sessions to interact with children and assist them to practice and develop skills to address identified deficits in social-emotional and adaptive functioning, prosocial behavior, and emotional regulation. AAT sessions were recorded to code interactions at a later time.

Objectives

This study will address the following research questions:

1. How do children with autism ages 2 to 18 years interact with a live canine during AAT sessions?
2. How do children with autism ages 2 to 18 years interact with a toy plush dog during AAT sessions?

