3. Is there a difference in HAI in the live canine group and the toy plush dog group?
4. Is there a difference in prosocial behavior observed during AAT sessions between the live canine group and the toy plush dog group?
5. Is there a difference in behavior after AAT sessions between the live canine group and the toy plush dog group?

Design and Statistical Analysis Plan

We used two human-animal ethograms to investigate human-animal interaction and bonding occurring during AAT sessions. Prosocial behavior and emotional regulation demonstrated by participants outside of AAT sessions were assessed by two self-report questionnaires completed by caregivers. SPSS and Microsoft Excel were used to calculate the analysis. Descriptive statistics were utilized to compare prosocial behavior and emotional regulation occurring apart from AAT sessions between the two groups. Poisson analysis was conducted to examine human-animal bonding and human behavior occurring during AAT sessions. Independent *t*-tests were used to analyze the differences in human-animal interaction between the two groups. The homogeneity of the variance (HOV) assumption between two groups was checked using Levene's test for equality of variances in SPSS program before conducting the *t*-tests analysis. Results of *t*-tests with adjusted degrees of freedom value were reported if the HOV was violated. The null hypothesis was set to reflect no significant difference in HAI between groups for the independent *t*-tests; therefore, a significant difference in the human-animal interaction and human behaviors regarding the inclusion or exclusion of the canine could be confirmed if the *t*-test results reject the null hypothesis. Cohen's *d* was used to report the effect sizes of the independent *t*-tests; values up to 0.20 were interpreted as small, 0.50 as medium, and 0.80 as large effect sizes. Analysis of variance was used to assess differences between the two groups in prosocial behavior and emotional regulation occurring apart from AAT sessions.

Methods

Demographic data; past, family, and social histories; and prior therapy evaluations were collected during the initial consultation for enrollment into the ASD program. Additionally, pet ownership in the family home was included in the analysis.

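### Entering only the modal intensity code in the analysis loses information on the ethogram's intensity measure, by an amount the documents do not fix; a per-domain mean or an ordinal model would use every code

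*Combined protocol and SAP*

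**What the plan says.** In the Methods section, the paragraph on the 3-AAT Observation ethogram lists three features of each interaction between child and canine: frequency, intensity and duration. On intensity it says: "Each interaction has a code for intensity from 0 (not intense) to 3 (the most intense"). It then says that "the mode of the interaction was entered to run the analysis". The other two features are recorded separately: "Frequency is measured by a tally count and duration is assessed by rounding either up or down to the nearest 30 second mark". The ethogram has six domains of human interaction, among them affection and withdrawal, and 24 subdomains.

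The Design and Statistical Analysis Plan section says that independent t-tests "were used to analyze the differences in human-animal interaction between the two groups", and that "Poisson analysis was conducted to examine human-animal bonding and human behavior occurring during AAT sessions". It does not say which of these uses the intensity mode. Nor does the plan give a reason for choosing the mode, the unit over which it is taken, or a rule for ties.

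**The concern.** The third research question asks whether human-animal interaction differs between the live-canine and plush-toy groups, and intensity is one of the features by which the ethogram describes that interaction. Reducing a set of four-level codes to the most common one has three consequences.

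- It ignores every interaction that is not in the most common category.
- It does not move until the most common category changes, so a real shift in intensity can leave it where it was.
- It need not be unique. Without a tie rule, software or the coder decides the value.

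At stake is the chance of seeing a true group difference in intensity, and whether a second analyst would get the same result from the same codes.

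**Working it through.** **What the mode misses.** Two constructed children, ten interactions each, with counts of codes 0/1/2/3:

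- Child A, 3/4/3/0: mode 1; mean (0×3 + 1×4 + 2×3)/10 = 1.0.
- Child B, 0/4/3/3: mode 1; mean (1×4 + 2×3 + 3×3)/10 = 1.9.

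The means differ by 0.9 on a 0–3 scale and the modes are equal. A third child with counts 4/1/1/4 has mode 0 or mode 3, depending on an unstated rule.

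**Inputs.** The documents give the 0–3 scale, the use of the mode, the t-test, and Cohen's d labels ("values up to 0.20 were interpreted as small, 0.50 as medium, and 0.80 as large effect sizes"). They give no alpha, target power, target effect, distribution of intensity codes, number of interactions per child or within-child correlation, so there is no stated power figure to reproduce. The only head count is 150 children in the Subjects table of the IRB form. The allocation ratio is not stated ("Participants were divided into two groups: one with a therapy canine and one with a plush toy dog"). Assumed here: two-sided 0.05, equal groups, and d of 0.2 to 0.8.

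**Analytic check.** With n per group, power ≈ Φ(d√(n/2) − 1.96). If the mode has relative efficiency r against the mean, d becomes d√r. For n = 75, √(75/2) = 6.124.

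- d = 0.5: Φ(3.062 − 1.96) = 86.5%. With r = 0.7: Φ(2.562 − 1.96) = 72.7%, a loss of 13.8 points. With r = 0.9 the loss is 3.7 points; with r = 0.5 it is 28.3.
- d = 0.2: 23.1%; r = 0.7 costs 5.6 points.
- d = 0.8: 99.8%; r = 0.7 costs 1.5 points.

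The loss therefore depends on both the effect and r, and the documents give neither.

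**Simulation of r.** Latent normal intensities with a child effect were cut into codes 0–3. One mean and one mode (lowest code if tied) were taken per child, and each was compared between groups by an independent t-test. There were 75 per group, 5, 10 or 30 interactions per child, three sets of cut-points and 600 trials per setting. The Monte Carlo error of each power near 80% is about √(0.8×0.2/600) = 1.6 points.

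| Latent ICC | Loss at d = 0.5 (points) | Loss at d = 0.8 (points) |
|---|---|---|
| 0.9 | 2 to 7 | about 0 to 1 |
| 0.6 | 6 to 19 | 0 to 3 |
| 0.3 | 10 to 47 | 1 to 17 |
| 0.1 | 16 to 70 | 3 to 72 |

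The upper ends at ICC 0.6 and below come from cut-points that make most codes 0. Two rows at d = 0.5 and 10 interactions show this. At ICC 0.9 with even cut-points, power is 82.0% for the mean and 79.5% for the mode. At ICC 0.3 with mostly zero codes, it is 79.8% and 45.0%. In 71 of the 72 settings the mean did at least as well as the mode; in the other, the mode was ahead by 0.2 points, within simulation error.

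A second set, with 30 or 75 per group and 5 to 20 interactions per child, gave losses of about 0 to 6 points at ICC 0.9, 5 to 20 at ICC 0.5, and 10 to 47 at ICC 0.2, depending on cut-points.

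**Ties.** With between-child SD 0.5 and within-child SD 1 (ICC = 0.25/1.25 = 0.2), about 12% to 30% of children had a tied mode; at ICC 0.8 ties fell to about 8%. In the ICC 0.2 settings, taking the highest instead of the lowest tied code changed the significance result in about 9% to 23% of simulated trials.

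**The case against.** The strongest objection concerns size. A reader who simulates with between-child SD 0.5 and one set of cut-points obtains a loss of 11 to 21 points, and might infer that this is the cost to the trial. The documents do not support that. They do not give the within-child consistency or the code distribution, and these two inputs move the answer from almost nothing to a very large loss. Intensity coded for one child with one canine could well be consistent. This objection stands.

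A reader might also infer that most of the intensity data are thrown away. That too depends on consistency: about 45% to 56% of codes were non-modal at ICC 0.2, but about 20% at ICC 0.9, where the mode keeps nearly all the between-child information. Nor is a loss shown for the trial's main comparison, because no primary outcome is named.

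A further objection is that a mode suits an ordinal code, while a mean imposes equal spacing. As a descriptive summary the mode is defensible. As input to a t-test it gains nothing on this score, because the t-test averages the modes and so assumes the same spacing. The plan does not say outright that the mode goes into the t-test, so the power argument is conditional on that. The gaps in unit and tie rule are not.

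Finally, one mean over all coded interactions would mix affection with withdrawal and be hard to interpret. That is correct, and the remedy has to work within domains.

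**Conclusion.** The point holds in limited form. The plan records an intensity code for every interaction and analyses a coarser summary whose unit and tie rule are not defined. If that summary enters the planned t-test, the intensity comparison loses power relative to the mean. The direction is consistent across the settings run. The size is not fixed by the documents: about 0 to 6 points at ICC 0.9, about 5 to 20 at ICC 0.5, and about 10 to 47 at ICC 0.2 or when most codes are 0. These figures assume 30 or 75 per group, 5 to 20 interactions per child, two-sided 0.05, and one mode per child. They are ranges over the settings tried, not bounds; at ICC 0.1 with mostly zero codes the loss reached about 70 points. The advantage was simulated for the mean only, not for an ordinal model. It is worth changing because the remedy is cheap, not because a particular loss has been shown.

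**What to change.** Within each ethogram domain, replace the mode with each child's mean intensity over all coded interactions, and use it in the same between-group test. Do not pool across domains. Alternatively, analyse the per-interaction codes in an ordinal mixed model with a child random effect, which avoids the equal-spacing assumption. Keep the mode as a descriptive summary, and state the unit over which it is taken and how ties are resolved. State which test uses the intensity variable, and how a child with no coded interaction in a domain is handled, since neither a mean nor a mode then exists.

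The cost is recomputing one summary variable per domain from codes already recorded; no new coding or data collection is needed. The mean treats the steps from 0 to 3 as equally spaced, as a t-test on the mode already does. Because the plan is written in the past tense and the study period has ended, any mode-based result already obtained should be shown beside the new one, with the change declared as made after data collection.
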